EFFECTS OF AN ELASTIC BANDAGE PROTOCOL IN INDIVIDUALS WITH CHRONIC ANKLE INSTABILITY

NCT number: unavailable

Date of document: May 22, 2020

Procedures: The volunteers will complete the sample characterization form containing the demographic data (age, sex, weight, height, BMI, dominance, level of physical activity, history of injuries in the lower limbs) and will sign the informed consent form. Then, they will answer the Cumberland Ankle Instability Tool questionnaire - brazilian-portuguese version and the American Orthopedic Foot and Ankle Society - Ankle-hindfoot Scale validated for Portuguese.

After characterization of the sample and randomization in certain groups, evaluations of static postural control will be carried out through the force platform (BIOMECH400, EMG System do Brasil, SP Ltda.) In unipodal support on the unstable ankle. In the assessment of postural control, participants will be instructed to remain in unipodal support, barefoot for thirty seconds looking at the horizon (a mark will be fixed on the wall at a height of 2 meters), with the upper limbs relaxed beside the body, free lower limb without touching the test limb, maintaining knee flexion position at 90°. Participants will perform the test three times with a 30-second rest interval between each run.

Subsequently, the Y Balance Test will be performed, which consists of reaching the greatest possible distance in three different directions (anterior, posterolateral and posteromedial) with the limb contralateral to the unstable ankle while this limb remains supported in the center of the intersection of measuring tapes in Y shape. (47) Each of the directions is tested three times and the 3 repetitions are averaged.

Finally, the side hop test will be performed, which consists of one-legged lateral jumps over a distance of 30 cm between markings on the ground. There will be 10 jumps, which will be counted from the starting point until the return to it. Participants will be instructed to perform as quickly as possible. In the event of a fall, touch of the pending limb to the ground or failure to pass the mark, the test will be discarded and performed again.

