Performed the three postural control tests, an elastic bandage will be applied on the ankle with instability or on the ankle with the lowest score on the CAIT questionnaire (in case of bilateral instability), if there is bilateral instability with the same score on the CAIT-p, bandaging will be performed in the dominant lower limb. The application area will be previously free of hair (performing trichotomy) and asepsis with 70% alcohol. The technique used will be the “technique for stabilizing the ankle”, where an “I” tape without a fixed point is placed from one malleolus to the other by the hindfoot and another “I” tape without a fixed point involves the ankle joint, starting from the calcaneal tendon to cross in front of the talus. The application will be carried out by a professional qualified by the Therapy Taping Method®.

After applying the bandage, the volunteers will again perform the tests mentioned above. They will be instructed on how to care for the bandage (do not dry the area by rubbing the towel, but with light touches, do not cut the ends of the bandage if they are peeling off, do not remove and replace the bandage) to preserve the application and keep the application up to the room day after placed.

- Experimental group: the application of the bandage will be carried out weekly, for five weeks, in the individuals allocated to this group. Each week the tension of the tapes will be increased, increasing 5% of tension per week in relation to the initial length.

- Control Group: the application of the bandage will be carried out weekly, for five weeks, in the individuals allocated to this group. The applications will not suffer an increase in the tension of the tapes, they will only be placed on the application site.

Initial assessment will be carried out on the first day, reevaluations in the third week and in the sixth week after the initial assessment.

- Data analysis:

The normal distribution of the sample data will be analyzed using the Shapiro Wilk test. If normality is established, an analysis of variance of the factors will be used for each dependent variable to compare the groups (elastic bandage without tension and elastic bandage with tension) in both tasks. All statistical analyzes will be performed in the SPSS statistical program (version 20.0) with the adopted significance of 5% ($p < 0.05$).

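### The only planned group comparison depends on a Shapiro-Wilk test of undefined data and has no fallback; one pre-stated model adjusting for the day-1 value needs no such condition

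*Combined protocol and SAP*

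**What the plan says.** The Data analysis paragraph of the combined protocol and SAP opens: "The normal distribution of the sample data will be analyzed using the Shapiro Wilk test". It then makes its group comparison conditional on the result: "If normality is established, an analysis of variance of the factors will be used for each dependent variable". The last sentence of the paragraph gives only the software and the 5% significance level.

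Four things are left open:
- what is tested: raw values or model residuals, pooled or by arm, at which visit;
- what is done with an outcome that fails: no rank test, transformation or other model is named;
- which factors enter the ANOVA, and whether the day-1 value has any role;
- which outcomes are covered. The purpose given for the ANOVA is "to compare the groups (elastic bandage without tension and elastic bandage with tension) in both tasks", which counts two, but Procedures describes three tests ("Performed the three postural control tests"), one of them with three reach directions.

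On timing, Procedures says: "Initial assessment will be carried out on the first day, reevaluations in the third week and in the sixth week after the initial assessment". It also provides a retest straight after taping: "After applying the bandage, the volunteers will again perform the tests mentioned above".

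**The concern.** Read literally, an outcome that fails the normality check has no planned group comparison, and whatever is then run is chosen with the data in view. Two analysts who follow the text faithfully can also test different things, get different pass or fail results, and so run different analyses on the same outcome. Neither doubt can be removed after the event.

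The plan also gives no stated use to a measurement it already collects. All three tests are done before the tape is applied, so a pre-taping value of each outcome is available as a covariate.

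**Working it through.** The documents give no sample size, SD, effect size or correlation over time, so there is no figure to reproduce. Apart from the 5% level, every input below is assumed and the results are illustrative.

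**1. How often the check fails when data are normal.** Assume a 0.05 threshold and one pooled check per outcome. One force-platform measure, three Y Balance directions and one side hop score make 1 + 3 + 1 = 5 outcomes. The chance of at least one failure, if independent, is 1 − 0.95^k:
- k = 2: 0.098
- k = 4: 0.185
- k = 5: 0.226

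Simulated correlated outcomes (30 or 60 participants in total, correlation 0.3 or 0.5 between outcomes) give 0.220–0.247 for five.

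**2. How often it fails when data are skewed.** Log-normal data with log-SD 0.3 fail a pooled raw-value check in 25% of trials at 10 per arm and 65% at 30 per arm. The unit tested matters: at log-SD 0.5 and 20 per arm the failure rate is 84% (pooled raw), 76% (either arm) or 54% (residuals of the baseline-adjusted model). With 15 or 30 per arm, these three readings do not all agree in 13–16% of trials for normal data, 26–45% at CV 0.2 and 32–53% at CV 0.4.

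**3. Is the condition needed for type I error?** Simulated with no effect, 10 to 30 per arm, baseline correlation 0.7, normal to strongly skewed (log-SD 0.8), 4,000 trials per setting:
- unconditional ANOVA: 3.7–5.5%
- unconditional baseline-adjusted model: 4.0–5.6%

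The simulation standard error is √(0.05 × 0.95 / 4,000) = 0.34 points, so both are close to 5%.

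**4. Does the condition cost power?** Take the plan's own ANOVA, on follow-up values, as the analysis after a pass and Mann-Whitney after a failure. Over eight skewed settings (CV 0.2 or 0.4, 15 or 30 per arm, correlation 0.5 or 0.7, shift 0.6 SD), dropping the condition changes power by −0.1 to +1.3 points. At CV 0.4, 30 per arm and correlation 0.7 it is 57.7% with the condition and 58.3% without. A further simulation found under 1 point, for example 60.9% against 61.2%.

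**5. What does the day-1 value add?** With correlation ρ, the variance of the group difference relative to a follow-up-only ANOVA is 2(1 − ρ) for a change score and 1 − ρ² for the baseline-adjusted model. That is 1.00 and 0.75 at ρ = 0.5, and 0.60 and 0.51 at ρ = 0.7. For normal data and a 0.6 SD shift, approximate power is Φ(0.6 × √(n/2) / √v − 1.96), where v is that variance ratio:

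| n per arm, ρ | Follow-up only | Change score | Baseline-adjusted |
|---|---|---|---|
| 15, 0.5 | Φ(−0.317) = 38% | 38% | Φ(−0.063) = 47% |
| 15, 0.7 | 38% | Φ(0.161) = 56% | Φ(0.341) = 63% |
| 30, 0.5 | Φ(0.364) = 64% | 64% | Φ(0.723) = 77% |
| 30, 0.7 | 64% | Φ(1.040) = 85% | Φ(1.294) = 90% |

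The gains are about 10–26 points over follow-up only and 5–12 over the change score. The formula treats the variance as known, which makes it slightly optimistic. Simulation that estimates the variance and includes skewed data gives about 7–27 and 2–11 points.

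**The case against.** The best defence is that this is a short omission: name the fallback and the unit checked, and the gap closes without deleting anything. That largely stands. A fallback fixed in advance keeps type I error near 5%, and one that keeps the day-1 value comes within 1 point of the unconditional model's power on the original scale. Robustness without the condition is not special to the proposed model either, since plain ANOVA has it too.

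Three stronger readings are tempting, and the documents do not support them.

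- **That the normality condition itself costs much power.** Large differences appear only if baseline adjustment is put on one side of the comparison and not the other. With the plan's own ANOVA as the pass analysis, the cost is about 1 point.
- **That the plan certainly ignores day-1 data.** The wording speaks of factors in the plural and there are repeated assessments, so a group-by-time ANOVA is a fair reading. With two time points its interaction is the change-score test. On that reading the gain is the smaller one, about 2–11 points.
- **That false positives are inflated.** Simulated type I error reaches 5–9% only if the smallest of three p-values is taken after a failure, and nothing in the text suggests this.

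Two cautions also stand. Counting checks over five outcomes and three visits raises the chance of some failure to 1 − 0.95^15 = 54% under independence, but the condition works outcome by outcome and visits on the same person are correlated. And the documents do not show that any outcome is skewed; that is plausible for a side hop score if it is a time, and has no stated basis for Y Balance.

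**Conclusion.** The point holds in a limited form. The sole group comparison is conditional on a test of undefined data, and an outcome that fails has no planned analysis. The condition protects nothing in the settings examined, because type I error stays near 5% without it. Its harm is an undefined, data-dependent choice of analysis, not lost power or inflated error. The worthwhile power gain comes from a different change, adjusting for the day-1 value: about 7–27 points or about 2–11 points, depending on how the ANOVA is read. Those ranges rest on 15 or 30 per arm, correlation 0.5–0.7, a 0.6 SD shift and normal or log-normal data, none of which the documents supply. The textual gap does not depend on these assumptions. This should be corrected before outcome data are seen.

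**What to change.** Delete the normality condition. For each outcome, pre-state a linear model of the week-6 value with group as factor and the day-1 pre-taping value of that outcome as covariate, and report the adjusted difference with a 95% confidence interval. Analyse week 3 and the immediate post-taping value by the same model as secondary. Inspect model residuals for description only. A bootstrap or permutation interval is optional; if it is run outside SPSS, name the program.

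State that the day-1 tests precede taping but, by the order given in Procedures, follow randomisation.

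If the sponsor keeps the condition, the minimum is one check per outcome on model residuals and a named fallback that keeps the day-1 value.

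Separately, reconcile the two tasks in the analysis text with the three tests in Procedures. Multiplicity across outcomes and visits is a different matter and is not settled by this change.

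The cost is a few sentences and slightly more analysis work, with no new data. Naming week 6 as the main time point is the sponsor's choice and must be fixed before outcome data are seen.

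### The ANOVA names no covariate, time term or main visit, so the pre-tape value has no stated use; adjusting for it would be expected to gain precision over a follow-up-only or change-score comparison

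*Combined protocol and SAP*

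**What the plan says.** The Procedures section describes three tests: force platform, Y Balance Test and side hop test. They come after allocation: "After characterization of the sample and randomization in certain groups, evaluations of static postural control will be carried out". They also come before the first tape: "Performed the three postural control tests, an elastic bandage will be applied on the ankle with instability". They are then repeated the same day: "After applying the bandage, the volunteers will again perform the tests mentioned above". The later schedule is "Initial assessment will be carried out on the first day, reevaluations in the third week and in the sixth week after the initial assessment". Each person therefore has a pre-tape value of every variable and at least three later values.

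The Data analysis section gives a Shapiro-Wilk check and then one comparative method: "an analysis of variance of the factors will be used for each dependent variable to compare the groups". The factors are not listed. The only things identified are the two tape groups and an undefined pair of tasks: "to compare the groups (elastic bandage without tension and elastic bandage with tension) in both tasks". No time factor, group-by-time term, within-person term, covariate, change score or main visit appears. The level is given as "with the adopted significance of 5" percent.

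**The concern.** The sentence on analysis fits several different analyses, and they treat the pre-tape value differently. An ANOVA of values at a follow-up visit ignores it. An ANOVA of change scores subtracts it with a fixed slope of 1. A repeated-measures ANOVA uses it through the group-by-time term. The plan does not say which is meant, so the estimate and its precision are open until the analyst chooses.

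What is at stake is precision and a clear estimate, not validity. In a randomised comparison, leaving out the baseline does not bias the group difference. It can make the confidence interval wider than the collected data require. Without a main visit, it is also unclear which difference is the result for each variable.

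**Working it through.** **Inputs.** From the documents: two groups, a pre-tape value of each variable, and a 5% level (taken as two-sided). Not in the documents, so assumed and varied: total sample size N (20 or 40, split 1:1), correlation r between the pre-tape value and the value at the named visit (0 to 0.7), equal SD at each visit, and, for power, a true difference of 0.6 SD. The plan has no figure of its own to reproduce.

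**1. ANCOVA against follow-up-only ANOVA.** Variance ratio = (1 − r²) × (1 + 1/(N − 4)). The second factor is the cost of estimating the slope: 1 + 1/36 = 1.028 for N = 40, and 1 + 1/16 = 1.0625 for N = 20.

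| r | N = 40 | N = 20 |
|---|---|---|
| 0 | 1.03 | 1.06 |
| 0.2 | 0.99 | 1.02 |
| 0.3 | 0.94 | 0.97 |
| 0.5 | 0.77 | 0.80 |
| 0.7 | 0.52 | 0.54 |

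The ratio equals 1 at r = √(1/(N − 3)), that is √(1/37) = 0.16 for N = 40 and √(1/17) = 0.24 for N = 20. Below that, adjustment costs slightly more than it gains.

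**2. ANCOVA against a change score.** Variance ratio = ((1 + r)/2) × (1 + 1/(N − 4)). With N = 40 it is 0.67, 0.77 and 0.87 at r = 0.3, 0.5 and 0.7. Here the gain shrinks as the correlation rises.

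**3. Interval width and power, 20 per arm.** The unadjusted 95% CI half-width is t(38) × √(2/20) = 2.024 × 0.316 = 0.64 SD. With ANCOVA it is 0.65, 0.62, 0.56 and 0.46 SD at r = 0, 0.3, 0.5 and 0.7. Power for 0.6 SD (noncentral t) is 46% unadjusted, and 48%, 56% and 72% with ANCOVA at r = 0.3, 0.5 and 0.7.

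**4. Decaying correlation.** The r that matters is the one with the named visit. If correlation falls by a factor of 0.7 from each occasion to the next, pre-tape and week 6 are three steps apart, so r = 0.7³ = 0.343. The large-sample ratio is then 1 − 0.343² = 0.88, and power at week 6 is about 49%.

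**5. Group-by-time ANOVA.** Simulated power with four occasions, 20 per arm, equal correlations and the Greenhouse-Geisser correction (20,000 runs), against ANCOVA at one visit:

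| True difference | r = 0.3 | r = 0.5 | r = 0.7 |
|---|---|---|---|
| 0.6 SD at weeks 3 and 6 | 42% | 57% | 82% |
| 0.6 SD at all three post-tape occasions | 32% | 44% | 68% |
| Builds evenly to 0.6 SD at week 6 | 24% | 34% | 54% |
| ANCOVA, one visit with 0.6 SD | 48% | 56% | 72% |

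Neither test is uniformly better. Without the correction, under decaying correlation with adjacent value 0.7, the group-by-time test rejected a true null in 6.4% of 40,000 runs; with it, in 4.7%.

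**6. Mixed model with one common pre-tape slope.** Under decaying correlation the true slopes on the pre-tape value differ by occasion: 0.70, 0.49 and 0.34 at adjacent correlation 0.7. A model forced to one slope settles at 0.593. Its large-sample week-6 variance is 1 − 2 × 0.593 × 0.343 + 0.593² = 0.945, against 0.882 for ANCOVA. At adjacent correlation 0.5 the common slope is 0.333 and the variance is 1 − 2 × 0.333 × 0.125 + 0.333² = 1.03, worse than no adjustment. A mixed model therefore needs a pre-tape-by-occasion term.

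**The case against.** The strongest objection is that the plan speaks of factors in the plural and schedules repeated tests, so a group-by-time ANOVA is a natural reading, and that analysis does use the pre-tape value. This stands. A reader might infer that ANCOVA would usually be more precise than the planned analysis. The documents do not support that, because the planned analysis is not identified and, as step 5 shows, group-by-time power can exceed or fall short of single-visit ANCOVA. The precision statement holds only against follow-up-only and change-score analyses. Under the group-by-time reading, what remains is that the test is an omnibus one, that no visit-specific estimate is planned, and that no sphericity correction is mentioned.

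A reader might also infer that a group difference in the third or sixth week cannot be interpreted, because the plan does not say whether tape is worn at those tests. That is too strong. The randomised contrast stays valid; only its meaning, a worn-tape or a carry-over effect, is unclear. The plan has "the application of the bandage will be carried out weekly, for five weeks", and an unclearly worded instruction on how long to keep each application, so the sixth-week test may well fall after the last tape is off. It is not stated.

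Finally, every magnitude is assumed. A halving of the variance needs a correlation of about 0.7 with the named visit itself; with decay over time the gain at week 6 may be modest.

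**Conclusion.** The point holds as under-specification with a nearly free improvement. The documents name no covariate, time term or main visit, and state no use for a value that every participant provides. Read as a follow-up-only or change-score ANOVA, the analysis is valid and expected to be less precise than ANCOVA, provided that the correlation with the named visit exceeds about 0.16 (40 participants) to 0.24 (20) for the follow-up-only comparison. The gain over follow-up-only ranges from about 6% of the variance at 0.3 to about 48% at 0.7 with 40 participants. Read as a group-by-time ANOVA, the pre-tape value is not wasted and no general gain in power can be claimed; the gap is the missing visit-specific estimate and sphericity correction. These sizes rest on assumed sample sizes and correlations, equal SDs and 1:1 allocation. Nothing here makes the randomised comparison invalid.

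**What to change.** For each dependent variable, name one follow-up visit in advance and estimate the group difference with its 95% CI by ANCOVA, with group as factor and that variable's pre-tape value as covariate.

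If a mixed model over the post-tape occasions is used instead, include group, occasion, group-by-occasion, pre-tape value and pre-tape-by-occasion, with unstructured within-person covariance, and report the difference at the named visit. If a repeated-measures ANOVA is kept, test group-by-occasion with a sphericity correction (for example Greenhouse-Geisser) and add the baseline-adjusted estimate at the named visit.

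Three clarifications belong with this:
- State whether the third- and sixth-week tests are done with tape on, because this decides what the difference measures.
- Since randomisation precedes the pre-tape test, state that allocation is not disclosed before that test, so that the value is a sound baseline.
- Say which tests the two tasks in the Data analysis section are.

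**Cost.** A few lines of text, no new data and no more participants. The ANCOVA costs one degree of freedom and, if the correlation is near zero, a variance increase of about 3% (40 participants) to 6% (20). The mixed model costs more: three occasions need six covariance parameters and a pre-tape slope for each occasion, which is a consideration if the trial is small.

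### The plan does not say who is tested and analysed once taping stops; a complete-case ANOVA could be biased if drop-out both differs by arm and relates to performance

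*Combined protocol and SAP*

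**What the plan says.** All of this is in the combined protocol and SAP.

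- **Treatment course (Experimental group and Control group items).** In both arms "the application of the bandage will be carried out weekly, for five weeks, in the individuals allocated to this group". In the experimental arm only, "Each week the tension of the tapes will be increased, increasing 5% of tension per week in relation to the initial length". The control arm's tape stays without added tension.
- **Assessment schedule (before the Data analysis section).** "Initial assessment will be carried out on the first day, reevaluations in the third week and in the sixth week after the initial assessment". On day 1 the three tests are done before and again after the tape is applied, so there are four test occasions.
- **Data analysis.** After a Shapiro-Wilk check, and if normality is accepted, "an analysis of variance of the factors will be used for each dependent variable to compare the groups". The software is SPSS 20.0 and the significance level is 5%.

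Nothing in the document deals with stopping taping, withdrawal, testing after taping has stopped, the analysis set or missing visits. Visit is not named as a factor. No repeated-measures procedure or mixed model is named.

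**The concern.** The planned difference between the arms is tape tension, and rising tension is a plausible reason to stop. The outcomes are single-leg stance, reach and hopping on an unstable ankle, so a link between stopping and performance is also plausible. The documents establish neither link.

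The ANOVA can be read in two ways, and leavers are lost in both:

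- **Repeated measures over the visits.** The standard procedure deletes anyone with a missing visit, including the values they did provide.
- **Separate ANOVA at each visit.** Earlier data are kept for the earlier comparisons, but leavers are absent at week 6.

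Either way, the week-6 result could become a comparison of those who stayed instead of the groups as randomised. If poorer performers leave the tension arm more often, that arm looks better with no true effect. Outcomes that were never collected cannot be recovered later.

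**Working it through.** The plan gives no sample size, SD, effect size or drop-out rate, so there is no figure to reproduce. What can be checked is when bias arises and roughly how large it is.

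**Assumptions (none from the documents).** SD 1 at each occasion; correlation 0.6 between any two occasions; true group difference 0; higher score means better; drop-out occurs before week 6.

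**Step 1: closed form for an extreme case.** The lowest fraction p at week 3 leaves the tension arm and nobody leaves the other. With z the normal quantile of p and φ the normal density, the mean week-3 score of those who stay rises by φ(z)/(1−p).

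- p = 0.10: 0.1755/0.90 = 0.195
- p = 0.20: 0.2800/0.80 = 0.350

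The bias in any contrast is that rise times the contrast's covariance with the week-3 score.

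| Contrast | Multiplier | p = 0.10 | p = 0.20 |
|---|---|---|---|
| Raw week-6 score | 0.6 | 0.117 | 0.210 |
| Mean of four occasions | (1 + 3×0.6)/4 = 0.7 | 0.137 | 0.245 |
| Week 6 minus baseline | 0.6 − 0.6 = 0 | 0 | 0 |
| Week 3 minus baseline, complete cases | 1 − 0.6 = 0.4 | 0.078 | 0.140 |

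The zero for week-6 change depends on week 3 being equally correlated with baseline and with week 6.

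If the control arm loses half as many by the same rule, the week-6 bias falls to about 0.05 SD (10% against 5%) and 0.09 SD (20% against 10%, i.e. 0.210 − 0.117).

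**Step 2: graded drop-out.** Simulation with 400,000 per arm. The log-odds of leaving fall by 1 or 2 per SD of the driving score, calibrated to each drop-out rate. Entries are bias in the complete-case raw week-6 difference, in SD (slope 1 / slope 2).

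| Drop-out depends on | 10% v 0% | 20% v 5% | 30% v 10% | 20% v 20% |
|---|---|---|---|---|
| Arm only | −0.003 | 0.004 | −0.001 | 0.002 |
| Week-3 score | 0.051 / 0.087 | 0.071 / 0.113 | 0.096 / 0.140 | 0.000 / −0.001 |
| Unseen week-6 score | 0.093 / 0.143 | 0.127 / 0.182 | 0.165 / 0.234 | 0.003 / 0.000 |

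For change from baseline to week 6 at unequal rates, the bias is within 0.005 SD when drop-out follows the week-3 score, and 0.035 to 0.092 SD when it follows the unseen week-6 score.

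**Step 3: using all observed visits.** Week 6 is predicted from day 1 and week 3 within each arm and averaged over everyone, as a stand-in for a likelihood-based mixed model. At unequal rates:

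- drop-out follows the week-3 score: bias within 0.005 SD
- drop-out follows the unseen week-6 score: 0.054 to 0.154 SD remains

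The model therefore removes the bias only when drop-out depends on observed values. Testing people after they stop taping is what addresses the remainder.

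**The case against.** The strongest reply is that the document is silent, not wrong, and several firmer readings go beyond it.

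- **A reader might infer that the ANOVA spans the visits and deletes incomplete cases.** The text names only a group comparison. Listwise deletion follows from one possible choice of procedure.
- **A reader might infer that tension-linked drop-out is enough to bias the result.** It is not. When drop-out depended on arm alone, bias was within 0.004 SD even at 30% against 10%. Drop-out must also relate to the outcome, and the documents say nothing about tolerability or expected drop-out.
- **A reader might infer that people who stop are not followed.** The week-3 and week-6 tests are not made conditional on continued taping, so the text neither excludes nor retains them.
- **A reader might calculate that listwise deletion loses 19% when 10% miss each visit (1 − 0.9² = 0.19).** That assumes the two visits are missed independently. If those who leave miss all later visits and 10% have left by week 6, the loss is 10%.
- **The 0.2 SD case is close to the worst case**, and week-6 change from baseline shows about no bias under the same mechanism.

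All five stand as limits on the claim. They do not remove it. Leavers are missing from week 6 under either form of ANOVA, the plan does not specify a change-score analysis, and week-6 change is also biased if drop-out follows the unseen week-6 score. With complete data a mixed model and an ANOVA test much the same effects, so the case for changing the model rests on the missing visits.

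**Conclusion.** The point holds conditionally. The plan leaves open whether visit is a factor, who is analysed, how missing visits are handled, and whether participants who stop taping are still tested. The group comparison could be biased if three conditions hold together: the analysis is complete-case, drop-out differs by arm, and drop-out relates to performance.

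Under the assumed SD of 1 and correlation of 0.6, a realistic order of size for the raw week-6 difference is 0.05 to 0.14 SD when drop-out follows the week-3 score. It is 0.09 to 0.23 SD when drop-out follows the unseen week-6 score. Bias is near 0 if drop-out depends on arm alone, or works in the same way and at the same rate in both arms. None of these figures predicts this trial, because the documents give no drop-out rate, SD or sample size.

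The change is worth making because it is cheap and the visits are already scheduled. The silence does not show that the trial will be biased.

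**What to change.** 1. **Follow-up.** State that everyone randomised is tested at weeks 3 and 6 whatever their taping status, and is analysed in the allocated group. The week-6 test falls after the five-week course, so it does not depend on continued taping.
2. **Model.** For each outcome, use a linear mixed model (the MIXED procedure in SPSS) with group, visit and group-by-visit, the pre-tape day-1 value as baseline, and a stated covariance structure, using all observed visits. Say whether the after-tape day-1 test enters as an occasion of its own, and name the week-6 group contrast to be reported.
3. **Reporting.** Give the numbers who stop taping, the numbers who miss each test, and the reasons, by group.
4. **Sensitivity analysis.** Allow for data missing not at random, for example by shifting the missing week-6 values of one arm over a stated range. A shift of d in a fraction p of an arm moves that arm's mean by p × d, so the shift that would change the conclusion is easy to show.

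The cost is a few sentences of protocol text, a different procedure in the same software, some effort to recall people who have stopped taping, and slightly more analysis work.
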